10.4.17 Time from First Dosing Date to the First Mean Hemoglobin Response

To measure the time to the first hemoglobin response (for the ≥ 1.0 g/dL criterion) in the absence of transfusions, both 12-week and 24-week rolling methods mentioned from section 10.4.12 will be applied.

The descriptive statistics for the time from first dosing date to the first 12-week (or 24-week) mean hemoglobin increase response (for the ≥ 1.0 g/dL criterion) will be provided by treatment group, where time from first dosing date to the first Hb increase response is defined as First Day of 12-week (or 24-week) Response – Date of First Study Drug +1. The difference in time from the first dosing date to the first Hb increase response (luspatercept – placebo), corresponding 95% CI and p-value will be calculated by t-test. Only subjects who have a response will be included.

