9.6.3.12. Duration of Mean Hemoglobin Increase from Baseline ≥ 1.0 g/dL

Descriptive statistics will be generated for the duration of mean hemoglobin increase for each treatment group. Kaplan-Meier method will be used for censored subjects. No statistical test will be performed to compare the 2 groups.

The duration will start from the first day of the first rolling 12-week window that achieves mean Hb increase from baseline ≥ 1.0 g/dL. It will end with the last day of the last consecutive rolling 12-week window that maintains mean Hb increase from baseline ≥ 1.0 g/dL.

9.6.3.13. 6MWT: Mean Change at Week 24 and 48

Mean changes from baseline at Weeks 24 and 48 will be analyzed using ANCOVA method with treatment group and randomization stratification factor(s) in the model and baseline 6MWT value as the covariate. In addition, subgroup of subjects with baseline 6MWT ≤ 450 meter will be performed.

Mean changes from baseline at Week 48 will be analyzed similarly.

9.6.3.14. Proportion of Mean Hemoglobin Increase From Baseline ≥ 1.5 g/dL at Week 13 to 24

Similar to the primary efficacy analysis, the proportion of subjects who have an increase from baseline ≥ 1.5 g/dL in mean of hemoglobin values over a continuous 12-week interval from Week 13 to Week 24 will be performed on the ITT population. Cochran-Mantel-Haenszel (CMH) test will be performed with randomization stratification factor(s) in the model to compare the treatment and placebo groups at 2-sided 0.05 level.

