5.2.1. Intent-to-Treat Population

The intent-to-treat (ITT) population will consist of all randomized subjects regardless of whether or not the subject received IP. All efficacy analyses will be conducted for the ITT population and will be analyzed based on randomization treatment.

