10 EFFICACY ANALYSIS

All efficacy evaluations will be conducted using the ITT population with the exception of FACIT-F Fatigue Subscale (SF) and SF-36 analyses that will be conducted on the HRQoL evaluable population. NTDT-PRO T/W and SoB scores will be analyzed by both ITT and HRQoL populations. The primary and key secondary endpoints will also be analyzed based on the Per Protocol population as a sensitivity analysis.

Some continuous variables like hemoglobin and weekly NTDT-PRO T/W and SoB domains will be derived as the sum of results over 12 weeks divided by the number of assessments. The mean over 12 weeks will be used to derive mean change from baseline for each subject.

For the early treatment-discontinued subjects, i.e. subjects who did not complete 24 weeks or 48 weeks of double-blinded treatment period, the transfusion and assessment records (including Hb and QoL) will still be collected up to 48 weeks post Dose 1 Day 1 or 9 weeks post last dose, whichever is the later date. All the assessments before the efficacy cutoff date will be used to evaluate primary and secondary endpoints. For these endpoints, if at the time of data summary, a subject has died or has not reached the end of the 12-week interval, this subject will be included in the analysis. For other efficacy endpoints, the collected records will be used (by visits or at specified time point) as needed, depending on the purpose of the summary. Please refer to the individual endpoint section for details.

The efficacy cutoff date is defined as the minimum date among death date, study discontinuation date, last dose date + 20, and data cutoff date. For the primary and responder-related secondary endpoints, if at the time of data summary, a subject's efficacy cutoff date is before the end of the 12-week interval or a subject has any invalid hemoglobin records (i.e., within 21 days following a transfusion) during the specified 12-week interval, this subject will be included in the analysis and his/her responder status will be classified in accordance with the definition of erythroid response in Section 10.2. For other efficacy endpoints, if a subject's efficacy cutoff date is before the end of the 12-week interval, the subject will be included in the analyses.

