10.4.12 Hemoglobin Increase from Baseline ≥ 1.0 g/dL Response Based on Rolling Method

The hemoglobin response will be measured using the consecutive “rolling” 12-week and 24-week time intervals within the entire study period up to the efficacy cutoff, i.e., Days 2 to 85, Day 3 to 86 for 12-week (or Day 2 to 169, Day 3 to 170 for 24-week) and so on. Note that, Day 1 hemoglobin belongs to baseline. The hemoglobin response is defined as subjects with ≥ 1.0 g/dL increase in mean from baseline during any consecutive rolling 12-week (or 24-week) time interval in the absence of transfusion. The Hb values within 21 days following a transfusion may be influenced by the transfusion and will be excluded from this analysis.

The treatment comparison with “rolling” method (luspatercept versus placebo) will be conducted by the CMH test stratified by the randomization stratification factors. The OR (luspatercept versus placebo) with corresponding 2-sided (at 0.05 alpha level) 95% CI and p-value will be provided. The number and percentage of responders will be summarized by each treatment group and the difference in proportions (luspatercept – placebo) and corresponding 95% CI will also be calculated by exact unconditional test with “rolling” method as well.

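### SAP 10.4.17 tests time to first hemoglobin response between arms among responders only, which is not a randomized comparison and can be biased in either direction

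*SAP*

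**What the plan says.** SAP 10.4.17 measures the time from first dose to the first day of the first window in which mean hemoglobin has risen by at least 1.0 g/dL without transfusion; "both 12-week and 24-week rolling methods mentioned from section 10.4.12 will be applied". It plans descriptive statistics by arm, then adds the difference (luspatercept minus placebo), for which the "corresponding 95% CI and p-value will be calculated by t-test". The paragraph closes with "Only subjects who have a response will be included". The p-value is not labelled descriptive, the type of t-test is not named, and no analysis of onset in all randomized subjects goes with it.

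The general rules read differently. SAP 5.2.1 states "All efficacy analyses will be conducted for the ITT population and will be analyzed based on randomization treatment", and SAP 10 states "All efficacy evaluations will be conducted using the ITT population", excepting only the FACIT-F and SF-36 analyses. SAP 10.4.12 compares the proportion with a rolling response, a comparison that "will be conducted by the CMH test stratified by the randomization stratification factors". For duration of response, Protocol 9.6.3.12 uses Kaplan-Meier and says "No statistical test will be performed to compare the 2 groups".

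**The concern.** Whether a subject responds is an outcome of treatment, so keeping only responders discards the balance that randomization provides. If luspatercept turns some subjects into responders who would not respond on placebo, the luspatercept responders are a mixture and the placebo responders are not. A difference in mean onset then arises from the mixture alone, even if the drug changes no one's timing among those who would respond on either arm.

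A reader could take the resulting p-value as evidence that luspatercept acts faster, or slower, than placebo. SAP 10.4.12 tests whether subjects respond, not when, so it does not correct that reading.

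**Working it through.** **1. The plan's own figure.** SAP 10.4.17 gives no number, but SAP 4.4 supplies the response rates and arm sizes: 50% vs 10%, 100 vs 50 subjects, two-sided alpha 0.05, 10% dropout. Power for two proportions is 0.9998 at 100/50 and 0.9995 at 90/45 after dropout. Both agree with the stated minimum of 99%.

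**2. Who is compared.** Expected responders are 100 × 0.50 = 50 and 50 × 0.10 = 5. The placebo count has a 95% binomial range of 1 to 9. The chance of fewer than two, which leaves no placebo variance, is 0.9^50 + 50 × 0.1 × 0.9^49 = 0.0052 + 0.0286 = 3.4%. The rates refer to the fixed Weeks 13-24 window. If rolling windows raise the placebo rate to 20% or 30% (assumed), the count becomes 10 (5 to 16) or 15 (9 to 22).

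**3. What the difference estimates.** Let a share pP respond on either arm with mean onset m0, unchanged by treatment. Let luspatercept add a share pL - pP with mean onset m1. The luspatercept responder mean is [pP·m0 + (pL - pP)·m1] / pL. Subtracting m0 gives

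expected difference = (1 - pP/pL) × (m1 - m0).

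At the planned rates the factor is 1 - 0.10/0.50 = 0.8. The sign depends only on whether the added responders start later or earlier than the others.

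**4. Simulated trials.** Onset times are assumptions. There were 20,000 trials per row; those with fewer than two responders in an arm (about 3.5%) were skipped. A 12-week window (Days 2-85) spans 84 days, so the last window inside 48 weeks starts on Day 336 - 83 = 253. For 24-week windows (168 days) it is Day 336 - 167 = 169.

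| Assumed onset | Formula (days) | Simulated (days) | p<0.05, pooled / Welch |
|---|---|---|---|
| Same in both arms, exponential, mean 60 | 0 | 0 | 4.7% / 12.4%, either direction |
| 10% with mean 40 in both arms; luspatercept adds 40% with mean 80 | 0.8 × (80 - 40) = +32 | +32.0 | 2.9% / 43.4% against luspatercept |
| As above, onsets after Day 253 dropped | - | +23.1 | 4.4% / 34.7% against |
| As above, onsets after Day 169 dropped | - | +14.8 | 5.2% / 25.1% against |
| Constant hazards giving 50% and 10% by Day 253 | 112.0 - 124.3 = -12.3 | -12.2 | 5.6% / 6.2% for luspatercept |
| 10% uniform on Days 2-253 in both arms; luspatercept adds 40% with mean 40 | 0.8 × (40 - 127.5) = -70 | -70.5 | 63.6% / 35.3% for luspatercept |

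The difference was positive in 92.7%, 87.9% and 81.4% of trials in the second, third and fourth rows.

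In the constant-hazard row the means are 1/λ - 253(1 - p)/p with λ = -ln(1 - p)/253. That gives 365.0 - 253.0 = 112.0 and 2401.3 - 2277.0 = 124.3. The hazard ratio for response is 0.6931/0.1054 = 6.6, yet the responder-only test finds it in about 6% of trials.

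**5. Contrast with an all-randomized analysis.** Two uniform patterns were run with the pooled test:

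- Would-respond-anyway subjects on Days 2-30 and added responders on Days 20-150: 0.8 × (85 - 16) = +55 days, significant for placebo in 88% of trials.
- Days 2-240 and Days 2-60 respectively: 0.8 × (31 - 121) = -72 days, significant for luspatercept in 74%.

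A log-rank test on all 150 subjects, with non-responders censored, favoured luspatercept in 99.7% and 99.95% of 2,000 trials respectively, and in 100% under constant hazards.

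**6. Other response rates.** At placebo/luspatercept rates of 20/60, 30/70 and 30/50%, the first uniform pattern gives +46, +39 and +28 days and the second gives -60, -51 and -36. The sign reversal remains.

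**The case against.** Several points on the other side are fair.

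- SAP 10 lets individual endpoint sections define which records they use, and 10.4.7 also restricts an ITT-based analysis to a subset. Section 10.4.17 states its set openly, and a non-responder has no onset time unless censoring is introduced. The conflict with the ITT rule is therefore supporting evidence only.
- Protocol 9.6.3.12 governs duration, and the visible protocol has no time-to-response endpoint. The comparison is an analogy, not a contradiction.
- SAP 10.4.18 models hemoglobin change over time in both arms without a responder restriction, which limits reliance on 10.4.17. It does not estimate when a response begins.
- The 50% and 10% rates are not rolling-window rates. At an assumed 60% vs 30%, the Welch rejection rate under identical onset falls from 12.4% to about 6%. The selection effect remains: the mean-40/mean-80 pattern still gives (1 - 0.30/0.60) × 40 = +20 days.
- Day 253 is an assumed bound, since the rolling windows run to the efficacy cutoff, which may fall after Week 48.
- In the two rows with negative differences, luspatercept does produce more and earlier responses across all randomized subjects, so a result in its favour is not wrong in direction. Only the late-onset patterns reverse it.

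These points limit the weight of the simulated figures. None makes the responder-only test a randomized comparison.

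**Conclusion.** The concern holds, at minor severity. As written, SAP 10.4.17 attaches a CI and p-value to a comparison of subsets formed after randomization, expected to be about 50 against about 5. The bias can favour either arm, from +32 to -70 days in the main illustrations. It is not inevitable: if added and other responders share the same onset distribution, the expected difference is zero.

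The sizes rest on assumed onset times and on applying the planned Weeks 13-24 rates to rolling windows. They show that the direction is open; they do not predict this trial's result. The analysis is outside the gatekeeping of SAP 10.1 and the visible endpoint list in SAP 4.2.2, so the primary and key secondary conclusions are untouched.

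**What to change.** Delete the between-arm difference, CI and p-value from SAP 10.4.17. Keep time to first response among responders as descriptive statistics by arm. This removes one sentence and needs no new programming.

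If the arms are to be compared on onset, use all ITT subjects, with Kaplan-Meier or cumulative incidence curves and a log-rank or Cox analysis stratified by the randomization factors. A response is dated to the first day of its window, so non-responders should be censored at the first day of their last evaluable window: efficacy cutoff minus 83 days for 12-week windows, minus 167 days for 24-week windows. State the rule for subjects with no evaluable window or no dose.

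The efficacy cutoff is the "minimum date among death date, study discontinuation date, last dose date + 20, and data cutoff date", so it depends on treatment discontinuation and censoring may be informative. Add a sensitivity analysis with death and treatment discontinuation as competing events. The cost is one standard program; the windows and cutoff are already derived for other analyses.

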10.4.18 Longitudinal Analysis of Hemoglobin Mean Change from Baseline

A mixed effect repeated measure model will be used with intercept and time as the random effect to evaluate the hemoglobin change from baseline at Weeks 12, 24, 36 and 48. The model includes the weekly change from baseline up to Week 48, and treatment group assignment, time (weeks since Dose 1 Day 1), baseline hemoglobin, randomization stratification factor(s), time-by-baseline score, and time-by-treatment group assignment terms in the model. The unstructured covariance matrix will be used to obtain the random effects variance components.

If the MMRM model using an unstructured covariance matrix fails to converge with the default Newton-Raphson algorithm, the Fisher scoring algorithm or another appropriate method will be used to provide initial values of the covariance parameters. In the rare event that none of the above methods yields convergence, a structured covariance, such as heterogeneous Toeplitz and Toeplitz structures, will be used to model the correlation among repeated measurements. In this case, the empirical option will be used because the sandwich variance-covariance estimator is asymptotically consistent.

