Mean NTDI-PRO (T/W domain) change from baseline over a 12-week interval between Weeks 37 to 48 (nominal Dose 13 to Dose 17) will be analyzed using ANCOVA method with treatment group and randomization stratification factor(s) in the model as covariates.

The treatment-by-stratification-factor(s) interaction will be added to the ANCOVA model as a sensitivity analysis and results from this model will be compared to the primary fixed effects model (without the interaction effect). If the interaction is significant at a 2-sided 0.1-alpha level, the nature of this interaction will be inspected as to whether it is quantitative (that is, the treatment effect is consistent in direction but not in size of effect) or qualitative (the treatment is beneficial in some values of the stratification factor(s)). If the interaction effect is found to be quantitative, results from the primary fixed effect model will be presented. If the interaction effect is found to be qualitative, further inspection will be used to identify in what values of the stratification factor(s) the treatment is more beneficial.

10.4.5 FACIT-F Fatigue Subscale (FS) Response at Weeks 13 to 24 and Weeks 37 to 48

Proportion of subjects with an increase from baseline ≥ 3 in mean FACIT-F FS score, over Weeks 13 to 24 in the luspatercept group will be compared with the placebo group. The CMH test will be used with baseline FACIT-F FS category ≥ 37 versus < 37 as the stratum to compare the response rates between the 2 groups. The selection of 37 as a threshold is based on a Phase 2 Luspatercept study (A536-06) in which it corresponds to a NTDI-PRO T/W domain scores of 4. The corresponding 95% confidence interval for odds ratio will also be provided. Similar analysis will be performed for Weeks 37 to 48.

10.4.6 SF-36 v2: Mean Change from Baseline at Week 24 and Week 48

The SF-36 Version 2.0 (acute condition with 1-week recall period) is a self-administered instrument consisting of 8 multi-item scales that assess 8 health domains: Physical functioning (PF), Role-Physical (RP), Bodily Pain (BP), General Health (GH), Vitality (VT), Social functioning (SF), Role-Emotional (RE), and Mental Health (MH). Two overall summary scores, Physical Component Summary (PCS) and Mental Component Summary (MCS), will be calculated from the 8 health domains. The primary interests of the SF-36 are the PCS and MCS norm-based scores.

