Scores for each domain and composite summary scale of the SF-36 will be derived using the Quality Metric's Health Outcomes™ Scoring Software 5.1, a software designed to provide standardized scoring methods for the SF-36 based on the 2009 US general population normative data (*Maruish, 2011*). The scoring algorithm, using the 1998 US general population normative data as an example, for the SF-36 is shown in Appendix 18.3.3.

Summary statistics (n, mean, median, SD, range) for PCS and MCS norm-based scores along with the change from baseline will be summarized at Weeks 12, 24, 36, and 48 for each treatment group. The Norm-base scores will be used for domain analysis and the PCS analysis. The raw scores for each individual question and the calculated domain and component scores will be presented in the listings for SF-36.

A mixed effect repeated measure model will be used with intercept and time as the random effect. The model includes the change from baseline scores up to Week 48 as the outcome, and treatment group assignment, time (weeks since Dose 1 Day 1), baseline scores, randomization stratification factor(s), time-by-baseline score, and time-by-treatment group assignment terms in the model. The unstructured covariance matrix will be used to obtain the random effects variance components.

If the MMRM model using an unstructured covariance matrix fails to converge with the default Newton-Raphson algorithm, the Fisher scoring algorithm or another appropriate method will be used to provide initial values of the covariance parameters. In the rare event that none of the above methods yields convergence, a structured covariance, such as heterogeneous Toeplitz and Toeplitz structures, will be used to model the correlation among repeated measurements. In this case, the empirical option will be used because the sandwich variance-covariance estimator is asymptotically consistent.

To assess the extent of missing data at each assessment visit by treatment group, compliance rates for the SF-36 will be estimated on the ITT population separately based on the number of subjects included in the ITT population per treatment group who are eligible for assessment at a given scheduled visit. Subjects will be considered compliant with completion of the SF-36 assessment if at least half of the 36 items (i.e., ≥ 18 items) are completed.

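### The repeated-measures models for SF-36 and hemoglobin, read naturally, force a straight-line treatment difference over 48 weeks although results are wanted at specific weeks

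*SAP*

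**What the plan says.** SAP 10.4.18 (hemoglobin) and SAP 10.4.6 (SF-36 PCS and MCS) give essentially the same model.

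- Random part: "A mixed effect repeated measure model will be used with intercept and time as the random effect" and "The unstructured covariance matrix will be used to obtain the random effects variance components".
- Fixed part for hemoglobin, besides treatment group: "time (weeks since Dose 1 Day 1), baseline hemoglobin, randomization stratification factor(s), time-by-baseline score, and time-by-treatment group assignment terms in the model". For SF-36 time is defined in the same way: "time (weeks since Dose 1 Day 1), baseline scores". Neither section names a visit factor, a spline or a higher-order time term.
- Target for hemoglobin: "to evaluate the hemoglobin change from baseline at Weeks 12, 24, 36 and 48".
- Target for SF-36: the section is titled "SF-36 v2: Mean Change from Baseline at Week 24 and Week 48". Its figures at Weeks 12, 24, 36 and 48 are descriptive summaries.
- If the model does not converge, both sections call it an MMRM and say that "a structured covariance, such as heterogeneous Toeplitz and Toeplitz structures, will be used to model the correlation among repeated measurements".

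Protocol 9.6.3.7 gives a different SF-36 model. It has subject as the only random effect and drops interaction terms that are not significant.

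**The concern.** A random intercept with a random effect of weeks, plus one time-by-treatment term in weeks, is a random-coefficients model. Its mean treatment difference is a straight line, and an estimate at Week 24 or 48 is a point read off that line. If the effect builds early and then holds, the line is too low in the middle of the period and too high at the end. A reader of the Week 48 estimate could then see an effect that still seems to be growing.

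The MMRM label and the Toeplitz fallback describe something else: residual covariance across discrete visits. Two programmers could follow the same text and fit different models, with different Week 24 and Week 48 contrasts. Reading time as categorical does not repair the text, because a random effect of time with an unstructured matrix over as many as 48 weekly levels is not estimable here (counts below).

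At stake are the SF-36 PCS and MCS secondary endpoint, for which this is the only treatment-comparison model in the SAP, and a supportive hemoglobin analysis.

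**Working it through.** **The plan's own figures.** The plan gives no precision or power figure for either model. Its two power statements (at least 99% for the primary response, 91% for NTDT-PRO T/W) concern other analyses. By normal approximation they come to 99.98% and 92.0% with 100 and 50 subjects, and 99.95% and 89.2% with 90 and 45. They do not bear on this point.

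**Inputs from the documents.** Doses every 21 days, so hemoglobin falls mainly on a 3-weekly grid (Weeks 3, 6, ..., 48). SF-36 is completed every other dose (protocol 6.8), so a 6-weekly grid (Weeks 6, 12, ..., 48). Sample size 150 at 2:1, with 10% dropout.

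**Assumptions.** The documents give no time course. I set the plateau to 1 and used exponential approach, 1 - exp(-t/tau), or a linear ramp to the plateau. With tau = 2 or 4, about 95% of the plateau is reached by Week 6 or 12 (1 - exp(-3) = 0.95). A straight line is the control.

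**Method.** With balanced complete data, the fixed effects of a random intercept-and-slope model equal the ordinary least-squares line through the mean treatment differences. The bias at week t is that line at t minus the true difference.

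**One case by hand** (ramp to Week 12, 3-weekly grid). The differences are 0.25, 0.50 and 0.75 at Weeks 3, 6 and 9, then 1.

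- Mean week = 25.5; mean difference = (1.5 + 13)/16 = 0.90625.
- Sxx = 9 × 16 × (16² - 1)/12 = 3060.
- Sxy = 0.75 × 22.5 + 0.50 × 19.5 + 0.25 × 16.5 = 30.75.
- Slope = 30.75/3060 = 0.01005 per week.
- Week 12: 0.90625 - 13.5 × 0.01005 = 0.771, truth 1, bias -0.229.
- Week 24: 0.90625 - 1.5 × 0.01005 = 0.891, bias -0.109.
- Week 36: 0.90625 + 10.5 × 0.01005 = 1.012, bias +0.012.
- Week 48: 0.90625 + 22.5 × 0.01005 = 1.132, bias +0.132.

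**Bias as a percentage of the plateau**

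| Assumed shape | 3-weekly: Wk 12 | Wk 24 | Wk 36 | Wk 48 | 6-weekly: Wk 24 | Wk 48 |
|---|---|---|---|---|---|---|
| Exponential, tau = 2 | -4.3 | -2.1 | +0.3 | +2.8 | -0.9 | +0.9 |
| Exponential, tau = 4 | -8.4 | -6.2 | +0.5 | +7.4 | -4.4 | +4.1 |
| Ramp to Week 6 | -8.1 | -3.7 | +0.7 | +5.1 | 0 | 0 |
| Ramp to Week 12 | -22.9 | -10.9 | +1.2 | +13.2 | -8.3 | +8.3 |
| Exponential, tau = 8 | -6.9 | -10.4 | -0.5 | +12.4 | -9.0 | +8.6 |
| Ramp to Week 24 | +2.6 | -24.7 | -2.1 | +20.6 | -23.8 | +16.7 |
| Straight line | 0 | 0 | 0 | 0 | 0 | 0 |

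The first four rows are the plateau by about Weeks 6 to 12. The next two show slower rises.

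**Simulation check.** 150 subjects at 2:1, 10% dropout, plateau 1.5 g/dL, tau = 4, 3-weekly visits, 25 replicates. Assumed random-intercept variance 0.36, slope SD 0.006 per week, residual SD 0.5.

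| Week | 12 | 24 | 36 | 48 |
|---|---|---|---|---|
| Truth | 1.43 | 1.50 | 1.50 | 1.50 |
| Linear time | 1.29 | 1.40 | 1.50 | 1.61 |
| Categorical time | 1.45 | 1.50 | 1.48 | 1.48 |

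The SD of the estimates was 0.09 to 0.12 for linear time and 0.12 to 0.15 for categorical time. The categorical fit used a factor for each 3-weekly visit and kept the random intercept and slope for covariance, so its SDs are only a guide to the model proposed below.

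**Covariance parameters** (k visits, unstructured: k(k+1)/2). Four visits: 10. Sixteen 3-weekly visits: 136. Forty-eight weekly visits: 1,176. Random intercept and slope with residual: 4.

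**The case against.** The strongest reply is that linearity is inferred. The SAP never says linear or continuous, and the MMRM and Toeplitz wording suits discrete visits. That stands as far as it goes: the text is inconsistent rather than plainly linear. But the random effect of time in weeks and the single interaction term favor the linear reading, and nothing in either section would stop a programmer from fitting it.

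The response shape is also assumed. The dose-delay rule at hemoglobin of 11.5 g/dL or above (protocol Table 5) tends to cap hemoglobin. The escalation rule after two cycles (SAP 9.4.2) could allow later gains. A plateau by Weeks 6 to 12 is therefore plausible but not documented, and the sizes above are a range.

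The bias is similar in size to the sampling SD: in the simulation -0.14, -0.10, 0.00 and +0.11 g/dL, against 0.09 to 0.12. This is a trade of bias against variance. The bias is directional, however, and more subjects would not remove it.

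Three stronger readings are tempting and not supported:

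- *Every visit is misestimated.* The line crosses the curve near Week 36, where the error is under 4% of the plateau on the grids considered. Week 12 is usually understated but not always (ramp to Week 24: +2.6%).
- *SF-36 has no other inferential analysis.* SAP 10.4.6 and 14 refer to a separate HRQoL SAP, which may add some.
- *The main hemoglobin conclusions are affected.* The CMH tests and the ANCOVA on 12-week means impose no time shape, and neither repeated-measures model is in the fixed testing sequence.

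**Conclusion.** The point holds in a limited form. SAP 10.4.6 and 10.4.18 describe a random intercept-and-slope model under an MMRM label, and the natural reading gives a linear treatment difference where week-specific results are wanted. For a rise followed by a plateau, the fit generally understates Week 24 and overstates Week 48.

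For the 3-weekly hemoglobin grid and a plateau by about Weeks 6 to 12, a plateau of 1.0 g/dL would mean errors of about -0.04 to -0.23 g/dL at Week 12, -0.02 to -0.11 at Week 24 and +0.03 to +0.13 at Week 48. For SF-36 the range of about 0 to -9% at Week 24 and 0 to +9% at Week 48 extends to tau = 8. A slow ramp to Week 24 would exceed both ranges. There is no bias if the true difference is linear or if the plateau is reached by the first modelled visit.

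This is a worthwhile correction to a secondary endpoint and a supportive analysis. It does not threaten the trial's main result.

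**What to change.** In SAP 10.4.6 and 10.4.18:

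1. Map observations to a small set of windowed analysis visits, for example Weeks 12, 24, 36 and 48, which the SAP already uses for the SF-36 summaries. State how several hemoglobin values in one window are combined.
2. Fit visit as a categorical factor with treatment, visit-by-treatment, baseline, visit-by-baseline and the stratification factors. Use an unstructured within-subject covariance and no random slope. The Toeplitz fallback then makes sense as written.
3. Report LS-mean differences with 95% CIs at the target visits: Weeks 24 and 48 for SF-36, and Weeks 12, 24, 36 and 48 for hemoglobin.
4. Align protocol 9.6.3.7, including its rule for dropping interaction terms.

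If a continuous-time model is preferred, specify and justify a nonlinear time function.

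Cost: wording and window definitions, with no new data. The visit set must stay small, because an unstructured matrix over every hemoglobin visit is unworkable with about 150 subjects. Expect some loss of precision, of the order of SD 0.12 to 0.15 against 0.09 to 0.12 g/dL in the one scenario simulated.
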